1.2 Study objectives, endpoints and estimands

| Table 1-1 Objectives and related endp | oints |
|---------------------------------------|-------|
|---------------------------------------|-------|

| Objectives | Endpoints Endpoint for primary objective | |
|---|--|--|
| Primary objective | | |
| To evaluate the safety of remibrutinib (25 mg b.i.d.) in CSU patients | Overall safety data, assessed as treatment emergent adverse events during the study | |
| Secondary objectives | Endpoints for secondary objectives | |
| • To evaluate the efficacy of remibrutinib (25 mg b.i.d.) by evaluation of: | | |
| Change from baseline in UAS7 at Week 12 | Absolute change from baseline in UAS7 at Week 12 | |
| Proportion of participants achieve disease activity control (UAS7 ≤ 6) at Week 12 | • Achievement of UAS7≤ 6 (yes/no) at Week 12 | |
| Proportion of participants achieve complete absence of hives and itch (UAS7 = 0) at Week 12 | • Achievement of UAS7 = 0 (yes/no) at Week 12 | |
| • Change from baseline in ISS7 at Week 12 | Absolute change from baseline in ISS7 score at Week 12 | |
| Change from baseline in HSS7 at Week 12 | Absolute change from baseline in HSS7 score at Week 12 | |
| Proportion of participants achieve disease activity control (UAS7 ≤ 6) at Week 2 | Achieving early onset of disease activity control, as defined as achievement of UAS7≤ 6 (yes/no) at Week 2 | |

| 1 age 14 01 54 |
|------------------------|
| Study No. CLOU064A1301 |
| |

| Objectives | Endpoints |
|--|---|
| Proportion of participants achieve DLQI = 0-1 at Week 12 | No impact on participants' dermatology-quality of life, as defined by achievement of DLQI = 0-1 (yes/no) at Week 12 |
| Maintain disease activity control assessed as cumulative number of weeks with UAS7 ≤ 6 response | Achieving sustained disease activity control, assessed as cumulative number of weeks with an UAS7≤6 response between baseline and Week 12 |
| Angioedema occurrence-free weeks assessed by the cumulative number of weeks with AAS7 = 0 response | Number of weeks without angioedema, assessed by the cumulative number of weeks with an AAS7= 0 response between baseline and Week 12 |
| | |
| | |
| | |
| | |
| | |
| | |
| | |
| | |
| | |
| | |
| | |
| | |
| i | |

1.2.1 Primary estimand(s)

Primary estimand on safety as primary endpoint

The primary clinical question of interest regarding safety as the primary endpoint is: What is the effect of remibrutinib treatment on the incidence of treatment-emergent adverse events (i.e., events started after the first dose of study medication or events present prior to start of treatment but increased in severity based on preferred term) in adult participants with CSU who are inadequately controlled by H1-antihistamine and receiving a stable locally label approved dose of a second-generation H1-antihistamine, regardless of treatment discontinuation for any reason, non-compliance (interruption) to treatment, switch of background medication or intake of a different second-generation H1-antihistamine as rescue medication/ confounding prohibited medication?

The primary estimand on safety is described by the following attributes:

- 1. **Population:** participants with inadequa]tely controlled CSU despite treatment with secondgeneration H1-antihistamine treatment who have CSU duration ≥6 months, a UAS7 score ≥16, ISS7 score ≥6 and HSS7 score ≥6 in the last 7 days prior to start of treatment.
- 2. Endpoint: incidence of treatment-emergent adverse events.

| Novartis | Confidential | Page 16 of 54 |
|----------|--------------|------------------------|
| SAP | | Study No. CLOU064A1301 |

- 3. **Treatment of interest:** the study treatment (remibrutinib 25 mg b.i.d.) regardless of treatment compliance (discontinuation/interruption), with background medication of local approved second-generation H1-antihistamine, and a different second-generation H1-antihistamine as rescue medication.
- 4. **Summary Measurement:** the number and the proportion of participants with at least one treatment-emergent adverse event.
- 5. Handling of remaining intercurrent events:
 - Discontinuation of study treatment due to any reason: data collection will be maintained in the follow-up period. The data collected after these events will be used for analysis.
 - Treatment non-compliance (interruption), intake of rescue medication, or switch of background medication: ignore, i.e., data collection will be maintained and available measurements post-intercurrent event will be used as if they had been obtained under the treatment: Treatment policy strategy
 - Intake of strongly confounding prohibited medication (e.g., biologics treatment, cyclosporine, systemic corticosteroids): Treatment policy strategy
 - Administration of medications affecting the evaluation of potential risks, including: (a) anticoagulant/anti-platelet medications (other than acetylsalicylic acid up to 100mg/day or clopidogrel); (b) live attenuated vaccines; (c) strong cytochrome P (CYP) 3A4 inhibitors; (d) moderate/strong CYP3A4 inducers, (e) Oral breast cancer resistance protein (BCRP) substrates that may have increased exposure when co-administered with remibrutinib (defined as pitavastatin, rosuvastatin, sulfasalazine and ubrogepan): Treatment policy strategy
 - Intake of other prohibited medication: Treatment policy strategy

1.2.2 Secondary estimand(s)

Secondary estimand on efficacy as secondary endpoint: change from baseline in UAS7 score at Week 12

The secondary clinical question of interest regarding efficacy as secondary endpoint, change from baseline in UAS7 score at Week 12 is: What is the effect of remibrutinib treatment on the change from baseline in UAS7 score after 12 weeks of treatment in adult participants with CSU who are inadequately controlled by H1-antihistamine and receiving a stable locally label approved dose of a second-generation H1-antihistamine, regardless of treatment discontinuation for any reason or intake of a different second-generation H1-antihistamine as rescue medication and considering strongly confounding prohibited medication use as an unfavorable outcome?

The secondary estimand on efficacy as secondary endpoint, change from baseline in UAS7 score at Week 12 is described by the following attributes:

- 1. **Population:** participants with inadequately controlled CSU despite treatment with secondgeneration H1-antihistamine treatment who have CSU duration ≥6 months, a UAS7 score ≥16, ISS7 score ≥6 and HSS7 score ≥6 in the last 7 days prior to start of treatment.
- 2. Endpoint: change in UAS7 from baseline at Week 12.

| Novartis | Confidential | Page 17 of 54 |
|----------|--------------|------------------------|
| SAP | | Study No. CLOU064A1301 |

- 3. **Treatment of interest:** the study treatment (remibrutinib 25 mg b.i.d.) regardless of treatment compliance, with background medication of local approved second-generation H1-antihistamine, and a different second-generation H1-antihistamine as rescue medication.
- 4. Summary Measurement: the mean change from baseline.
- 5. Handling of remaining intercurrent events:
 - Discontinuation of study treatment due to any reason: Treatment policy strategy
 - Treatment non-compliance (interruption), switch of background medication, or intake of rescue medication as per protocol prior to Week 12: Treatment policy strategy
 - Intake of strongly confounding prohibited medication (e.g., biologics treatment at any time before Week 12, cyclosporine after Week 8, systemic corticosteroids after Week 8): Composite strategy (irrespective of potential occurrence of other intercurrent events)
 - Intake of other prohibited medication prior to Week 12: Treatment policy strategy

Secondary estimand on efficacy as secondary endpoint: UAS7 ≤6 response at Week 12 (Week 2, if applicable)

The secondary clinical question of interest regarding efficacy as secondary endpoint, UAS7 \leq 6 response at Week 12 is: What is the effect of remibrutinib treatment on the UAS7 \leq 6 response after 12 weeks of treatment in adult participants with CSU who are inadequately controlled by H1-antihistamine and receiving a stable locally label approved dose of a second-generation H1-antihistamine, regardless of treatment discontinuation for any reason or intake of a different second-generation H1-antihistamine as rescue medication and considering strongly confounding prohibited medication as an unfavorable outcome?

The secondary estimand on efficacy as secondary endpoint, UAS7 \leq 6 response at Week 12 is described by the following attributes:

- 1. **Population**: patients with inadequately controlled CSU despite treatment with secondgeneration H1-antihistamine treatment who have CSU duration ≥6 months, a UAS7 score ≥16, ISS7 score ≥6 and HSS7 score ≥6 in the last 7 days prior to start of treatment.
- 2. Endpoint: UAS7 \leq 6 response at Week 12.
- 3. **Treatment of interest:** the study treatment (remibrutinib 25 mg b.i.d.) regardless of treatment compliance, with background medication of locally approved second-generation H1-antihistamine, and a different second-generation H1-antihistamine as rescue medication.
- 4. Summary Measurement: the number and the proportion of participants with UAS7 ≤ 6 response at Week 12.
- 5. Handling of intercurrent events:
 - Discontinuation of study treatment due to any reason: Treatment policy strategy
 - Treatment non-compliance (interruption), switch of background medication, or intake of rescue medication as per protocol prior to Week 12: Treatment policy strategy
 - Intake of strongly confounding prohibited medication (e.g., biologics treatment at any time before Week 12, cyclosporine after Week 8, systemic corticosteroids after Week 8): Composite strategy (irrespective of potential occurrence of other intercurrent events)
 - Intake of other prohibited medication before Week 12: Treatment policy strategy

| Novartis | Confidential | Page 18 of 54 |
|----------|--------------|------------------------|
| SAP | | Study No. CLOU064A1301 |

Secondary estimand on efficacy as secondary endpoint: UAS7=0, DLQI=0-1 and AAS7=0 response at Week 12

Similar estimand approach will be implemented for these endpoints as for the UAS7 ≤ 6 response at Week 12.

Secondary estimand on efficacy as other secondary endpoints as defined in Table 1-1.

Similar estimand approach will be implemented for these endpoints as for the change from baseline in UAS7 score at Week 12.

2 Statistical methods

2.1 Data analysis general information

The statistical analysis will be performed by Novartis personnel, using SAS Version 9.4 or above.

Summary statistics for continuous variables will include N, mean, standard deviation, minimum, first quartile, median, third quartile, and maximum.

Summary statistics for categorical variables will be presented in contingency tables and will include frequencies and percentages.

The interim analysis may be conducted when all participants have completed their Week 24 visit or discontinued early. If the interim analysis is conducted, data available at the cut off date (including beyond Week 24) will be used for the analysis. The data cut off date for Week 24 interim analysis will be the date of Week 24 visit for the last participant completing Week 24 visit. For efficacy analyses, the data up to Week 24 visit for each individual participant will be included. For safety analyses and other summaries, all available data until the cut off date will be included.

The final analysis will be performed based on the final database lock when all participants have completed the study or discontinued early.

The "LOU064 25mg" will be used as treatment group name in this study.

2.1.1 General definitions

2.1.1.1 Baseline and post-baseline definitions

Baseline for safety is the last assessment (including unscheduled visits) obtained on or before the day of the first dose of study treatment. All assessments obtained after the first dose of study treatment are considered as post-baseline unless otherwise specified.

Baseline for efficacy is comprised of the 7 days prior to the day of the enrollment in treatment period for weekly scores (UAS7, HSS7, ISS7, AAS7,

etc.). For other assessments (DLQI,

etc.), baseline is the assessment on or before the day of the enrollment in treatment period.

2.1.1.2 Study Day 1 and Study Day

For safety analysis, the day of first dose of study treatment is defined as Day 1.

For efficacy analysis, the day of enrollment in treatment period is defined as Day 1.

All other study days will be labeled relative to Day 1.

- For event dates on or after Day 1, study day for a particular event date is calculated as [Date of event] [Date of first dose (for safety)/day of the enrollment in the treatment period (for efficacy)] + 1, i.e., Day 2, Day 3, etc., will be one day, two days, etc., after Day 1, respectively.
- For the dates before Day 1, study day for an event date is calculated as [Date of event] [Date of first dose (for safety)/enrollment in the treatment period (for efficacy)], i.e., Day 1, Day -2, etc., will be one day, two days, etc., before Day 1, respectively. Duration of an event will be calculated as (Event end date Event start date + 1).

The descriptor "Day 0" will not be used.

2.1.1.3 On-treatment period for safety assessment

The on-treatment period is defined as the period from the first date of dose intake of treatment to the last date of dose intake + a period of time accounting for remaining exposure to drug in relation to the potential pharmacodynamic effects of remibrutinib. It is the reference period for safety analyses on adverse events, laboratory, vital signs, etc.

Remibrutinib has a short half-life (5hrs). Due to the covalent-binding mode, pharmacodynamic effects, including target inhibition in tissues and cells is to be taken into account for determining the follow-up time after the last study drug dose, which is beyond 5 half-lives'. As a conservative measure, 28 days was selected.

The on-treatment period lasts from the date of first administration of study treatment to 28 days after the date of the last actual administration of the study treatment or the end of study where the end of study is either of the date of study discontinuation, or study completion, or safety follow-up completion or cut-off date, depending on participant's status.

2.1.1.4 Assessment window

Assessment window for weekly scores (e.g., UAS7, ISS7, HSS7, etc.) from eDiary data

For completers (i.e., participants completed Week 52 study treatment), the study weeks for assessment completed on eDiary up to Week 52 are defined based on the study days starting with Day 1 (day of the enrollment in treatment period). The study day for the eDiary date will be calculated as [Date of Diary] – [Date of day of the enrollment in treatment period] + 1 for post-baseline assessment and [Date of Diary] – [Date of day of the enrollment in treatment period] for baseline assessment.

| Novartis | Confidential | Page 20 of 54 |
|----------|--------------|------------------------|
| SAP | | Study No. CLOU064A1301 |

The analysis Week 1 through Week 51 of the treatment period will be derived based on scheduled visit day as defined in Table 2-1. eDiary data on or before Day -1 of actual Week 52 study visit will be used for weekly score calculation up to Week 51.

The analysis Week 52 score will be derived as Day -7 to Day -1 of actual Week 52 study visit day.

The analysis follow-up Week 1 to Week 4 will be derived based on the actual Week 52 study visit day as defined in Table 2-1.

| Study period | Analysis visit | Scheduled visit day | eDiary assessment window |
|--------------|----------------|---------------------|--------------------------|
| Treatment | Baseline | 1 | Day -7 to Day -1 |
| | Week 1 | - | Day 1 to Day 7 |
| | Week 2 | 15 | Day 8 to Day 14 |
| | Week 3 | - | Day 15 to Day 21 |
| | Week 4 | 29 | Day 22 to Day 28 |
| | Week 5 | - | Day 29 to Day 35 |
| | Week 6 | - | Day 36 to Day 42 |
| | Week 7 | - | Day 43 to Day 49 |
| | Week 8 | 57 | Day 50 to Day 56 |
| | Week 9 | - | Day 57 to Day 63 |
| | Week 10 | - | Day 64 to Day 70 |
| | Week 11 | - | Day 71 to Day 77 |
| | Week 12 | 85 | Day 78 to Day 84 |
| | Week 13 | - | Day 85 to Day 91 |
| | Week 14 | - | Day 92 to Day 98 |
| | Week 15 | - | Day 99 to Day 105 |
| | Week 16 | 113 | Day 106 to Day 112 |
| | Week 17 | - | Day 113 to Day 119 |
| | Week 18 | - | Day 120 to Day 126 |
| | Week 19 | - | Day 127 to Day 133 |

Table 2-1Assessment window for weekly scores based on eDiary (for
completers)

| Week 20 | 141 | Day 134 to Day 140 |
|---------|-----|--------------------|
| Week 21 | - | Day 141 to Day 147 |
| Week 22 | - | Day 148 to Day 154 |
| Week 23 | - | Day 155 to Day 161 |
| Week 24 | 169 | Day 162 to Day 168 |
| Week 25 | - | Day 169 to Day 175 |
| Week 26 | - | Day 176 to Day 182 |
| Week 27 | - | Day 183 to Day 189 |
| Week 28 | - | Day 190 to Day 196 |
| Week 29 | - | Day 197 to Day 203 |
| Week 30 | - | Day 204 to Day 210 |
| Week 31 | - | Day 211 to Day 217 |
| Week 32 | 225 | Day 218 to Day 224 |
| Week 33 | - | Day 225 to Day 231 |
| Week 34 | - | Day 232 to Day 238 |
| Week 35 | - | Day 239 to Day 245 |
| Week 36 | - | Day 246 to Day 252 |
| Week 37 | - | Day 253 to Day 259 |
| Week 38 | - | Day 260 to Day 266 |
| Week 39 | - | Day 267 to Day 273 |
| Week 40 | 281 | Day 274 to Day 280 |
| Week 41 | - | Day 281 to Day 287 |
| Week 42 | - | Day 288 to Day 294 |
| Week 43 | - | Day 295 to Day 301 |
| Week 44 | - | Day 302 to Day 308 |
| Week 45 | - | Day 309 to Day 315 |

| Novartis | ; |
|----------|---|
| SAP | |

| Week 46 | - | Day 316 to Day 322 | | |
|---------|-----|--|--|--|
| Week 47 | - | Day 323 to Day 329 | | |
| Week 48 | - | Day 330 to Day 336 | | |
| Week 49 | - | Day 337 to Day 343 | | |
| Week 50 | - | Day 344 to Day 350 | | |
| Week 51 | - | Day 351 to Day 357 | | |
| Week 52 | 365 | Day -7 to Day -1 of Week 52 study visit | | |

Note: Week 52 study visit is during treatment epoch. eDiary data on this day will not be taken in the analysis.

For participants early discontinued study treatment prior to Week 12, it is suggested to collect the eDiary data even after the participant discontinued from treatment per "Treatment policy strategy" (this part of data is named as "retrieved drop-out data"). The retrieved drop-out (RDO) data will be included in the weekly score derivation until Week 12, when treatment policy strategy is used for estimands.

For participants who discontinued the study treatment earlier than Week 52, assessment will follow rules as defined in Table 2-2 up to Week 52. After Week 52, weekly scores will not be derived even when the eDiary data are collected.

| Study period | Analysis visit | Scheduled visit day | eDiary assessment window | |
|--------------|----------------|---------------------|--------------------------|--|
| Treatment | Baseline | 1 | Day -7 to Day -1 | |
| | Week 1 | - | Day 1 to Day 7 | |
| | Week 2 | 15 | Day 8 to Day 14 | |
| | Week 3 | - | Day 15 to Day 21 | |
| | Week 4 | 29 | Day 22 to Day 28 | |
| | Week 5 | - | Day 29 to Day 35 | |
| | Week 6 | - | Day 36 to Day 42 | |
| | Week 7 | - | Day 43 to Day 49 | |
| | Week 8 | 57 | Day 50 to Day 56 | |
| | Week 9 | - | Day 57 to Day 63 | |
| | Week 10 | - | Day 64 to Day 70 | |

Table 2-2Assessment window for weekly scores based on eDiary (for early
treatment discontinued participants earlier than Week 52)

| Week 11 | - | Day 71 to Day 77 |
|---------|-----|--------------------|
| Week 12 | 85 | Day 78 to Day 84 |
| Week 13 | - | Day 85 to Day 91 |
| Week 14 | - | Day 92 to Day 98 |
| Week 15 | - | Day 99 to Day 105 |
| Week 16 | 113 | Day 106 to Day 112 |
| Week 17 | - | Day 113 to Day 119 |
| Week 18 | - | Day 120 to Day 126 |
| Week 19 | - | Day 127 to Day 133 |
| Week 20 | 141 | Day 134 to Day 140 |
| Week 21 | - | Day 141 to Day 147 |
| Week 22 | - | Day 148 to Day 154 |
| Week 23 | - | Day 155 to Day 161 |
| Week 24 | 169 | Day 162 to Day 168 |
| Week 25 | - | Day 169 to Day 175 |
| Week 26 | - | Day 176 to Day 182 |
| Week 27 | - | Day 183 to Day 189 |
| Week 28 | - | Day 190 to Day 196 |
| Week 29 | - | Day 197 to Day 203 |
| Week 30 | - | Day 204 to Day 210 |
| Week 31 | - | Day 211 to Day 217 |
| Week 32 | 225 | Day 218 to Day 224 |
| Week 33 | - | Day 225 to Day 231 |
| Week 34 | - | Day 232 to Day 238 |
| Week 35 | - | Day 239 to Day 245 |
| Week 36 | - | Day 246 to Day 252 |
| Week 37 | - | Day 253 to Day 259 |

| | Week 38 | - | Day 260 to Day 266 | | |
|---------------------------|---------|-----|--------------------|--|--|
| | Week 39 | - | Day 267 to Day 273 | | |
| | Week 40 | 281 | Day 274 to Day 280 | | |
| | Week 41 | - | Day 281 to Day 287 | | |
| | Week 42 | - | Day 288 to Day 294 | | |
| | Week 43 | - | Day 295 to Day 301 | | |
| | Week 44 | - | Day 302 to Day 308 | | |
| | Week 45 | - | Day 309 to Day 315 | | |
| | Week 46 | - | Day 316 to Day 322 | | |
| | Week 47 | - | Day 323 to Day 329 | | |
| | Week 48 | - | Day 330 to Day 336 | | |
| | Week 49 | - | Day 337 to Day 343 | | |
| | Week 50 | - | Day 344 to Day 350 | | |
| | Week 51 | - | Day 351 to Day 357 | | |
| | Week 52 | 365 | Day 358 to Day 364 | | |
| No further analysis visit | | | | | |

Assessment window for the assessments performed at study visit (e.g., DLQI, safety assessment except AEs, etc.) until Week 52

When the assessments are summarized by visit, they are based on the visit numbers as recorded in eDiary or eCRF except for early treatment discontinuation (ETD) visit, and study discontinuation (SD) visit. **ETD visit, SD visit** will be remapped to the scheduled visit. Safety follow-up visit or unscheduled visits will NOT be remapped (except for the unscheduled visit to be consider as baseline).

The assessment window is based on the study assessment schedule. The assessment schedule defined in the protocol is shown in Table 2-3. Note for Electrocardiogram (ECG), at Week 2, 12, 52 and SD visit pre and post dose assessments will be performed. ETD visit can be remapped to Week 24 only, and SD visit can be remapped to Week 2, 12 and 52.

| Visit name | BSL | Week 2 | Week 4 | Week 8 | Week 12 | Week 16 | Week 20 | Week 24 | Week 32 | Week 40 | Week 52 | ETD | SD |
|---|-----|----------------|--------|--------|----------------|---------|---------|---------|---------|---------|----------------|-----|----------------|
| Scheduled visit day | 1 | 15 | 29 | 57 | 85 | 113 | 141 | 169 | 225 | 281 | 365 | - | - |
| Vital signs Clinical chemistry* Hematology Urinalysis | x | x | x | x | x | x | x | x | x | x | x | x | x |
| Coagulation Panel | х | | x | | х | | | x | | x | x | x | x |
| | | | | | | | | | | | | | |
| Weight | | | | | x | | | | | | x | x | x |
| Electrocardiogram (ECG) | х | X ² | | | X ² | | | x | | | X ² | x | X ² |
| DLQI | Х | | Х | | Х | | | Х | | | Х | Х | Х |
| | | | | | | | | | | | | | |

| Table 2-3 | Assassment schedule |
|-----------|---------------------|
| Table Z-S | Assessment schedule |

X: to be recorded, BSL: Baseline, ETD: Early treatment discontinuation, SD: Study discontinuation ¹ only post baseline

² pre and post dose

* C-reactive protein (CRP), estimated Glomerular Filtration Rate (eGFR): assessed at screening, baseline, weeks 12, 24 and 52. Fasting glucose assessed at baseline, weeks 2, 12 and 52.

The Table 2-4 shows the assessment window for the assessments performed at every visits (i.e., vital signs, clinical chemistry, hematology, urinalysis).

If more than one assessment fall into the interval,

- Then if there is the scheduled visit recorded in eDiary or eCRF, this visit will be chosen.
- If no, the earliest visit day will be chosen.

| Novartis | Confidential | Page 26 of 54 |
|----------|--------------|------------------------|
| SAP | | Study No. CLOU064A1301 |

For example, when a participant discontinued study treatment after completing Week 2 and Week 4, and ETD visit occurred on Day 35 and SD visit occurred on Day 80, the ETD visit will be mapped to Week 8 and SD visit will be remapped to Week 12.

If a participant visited the site earlier than scheduled visit day, e.g., Week 4 on Day 25 and ETD visit on Day 29, ETD visit will be remapped to Week 4. As the participant already performed Week 4 scheduled visit, the remapped Week 4 (ETD visit) will not be used.

If a participant visited the site late than scheduled visit day, e.g., Week 4 on Day 25, ETD visit on Day 58 and SD visit on Day 85, both ETD visit and SD visit will be remapped to Week 12. In this case, ETD visit will be used as Week 12, and Week 8 will be missing.

| Assessment visit | Scheduled visit Day | Assessment window |
|------------------|------------------------|--------------------|
| Week 2 | 15 | Day 2 to Day 15 |
| Week 4 | 29 | Day 16 to Day 29 |
| Week 8 | 57 | Day 30 to Day 57 |
| Week 12 | 85 | Day 58 to Day 85 |
| Week 16 | 113 | Day 86 to Day 113 |
| Week 20 | 141 | Day 114 to Day 141 |
| Week 24 | 169 | Day 142 to Day 169 |
| Week 32 | 225 | Day 170 to Day 225 |
| Week 40 | 281 | Day 226 to Day 281 |
| Week 52 | 365 | Day 282 to Day 365 |

Table 2-4Assessment window for vital signs, clinical chemistry, hematology,
urinalysis until Week 52

For the assessments which are not collected at every visit (e.g., DLQI etc.), assessment window will be combined. For example, DLQI is collected at Week 4, Week 12, Week 24 and Week 52. The assessment window will be combined as Table 2-5.

Table 2-5Assessment window for DLQI until Week 52

| Assessment visit | Scheduled visit day | Assessment window |
|------------------|------------------------|-------------------|
| Week 4 | 29 | Day 2 to Day 29 |

| Week 12 | 85 | Day 30 to Day 85 |
|---------|-----|--------------------|
| Week 24 | 169 | Day 86 to Day 169 |
| Week 52 | 365 | Day 170 to Day 365 |

Table 2-6 show the assessment windows of days for each assessment.

| | | | | - | | | | | | |
|---|--------|--------|--------|---------|---------|-------------|-------------|---------------------|-------------|-------------|
| Assessment visit | Week 2 | Week 4 | Week 8 | Week 12 | Week 16 | Week 20 | Week 24 | Week 32 | Week 40 | Week 52 |
| Scheduled visit day | 15 | 29 | 57 | 85 | 113 | 141 | 169 | 225 | 281 | 365 |
| Vital signs Clinical chemistry Hematology Urinalysis | 2-15 | 16-29 | 30-57 | 58-85 | 86-113 | 114- 141 | 142- 169 | 170- 225 | 226- 281 | 282- 365 |
| Coagulation Panel | 2-29 | | 30-85 | | 86-169 | | | 170-28 ⁻ | 1 | 282- 365 |
| | | | | | | | | | | |
| | | | | | | | | | | |
| Electrocardiogram (ECG) | 2-15 | 16-85 | | | 86-169 | | | 170-36 | 5 | |
| DLQI | 2-29 | | 30-85 | | 86-169 | | | 170-36 | 5 | |
| - | | | | | | | | | | |

 Table 2-6
 Assessment windows by assessment

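### If the SAP's earliest-visit tie rule also governs DLQI, the treatment-stop value can be reported as Week 12 in place of the retrieved drop-out value (minor, one descriptive endpoint)

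*SAP*

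**What the plan says.** **Protocol 9.1.1.** A participant who stops treatment before Week 12 has an ETD visit and is asked, where possible, to keep attending up to Week 12, when the SD visit is performed. DLQI is marked at both visits (protocol Table 8-1, SAP Table 2-3).

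**SAP 2.1.1.4, remapping.** Under the heading "Assessment window for the assessments performed at study visit (e.g., DLQI, safety assessment except AEs, etc.) until Week 52", ETD and SD visits "will be remapped to the scheduled visit. Safety follow-up visit or unscheduled visits will NOT be remapped", apart from an unscheduled visit that serves as baseline.

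**SAP 2.1.1.4, tie rule.** It follows the sentence "The Table 2-4 shows the assessment window for the assessments performed at every visits (i.e., vital signs, clinical chemistry, hematology, urinalysis" (closing bracket omitted). If more than one assessment falls in a window: "Then if there is the scheduled visit recorded in eDiary or eCRF, this visit will be chosen". The second limb is: "If no, the earliest visit day will be chosen". A worked example has ETD on Day 58 and SD on Day 85. Both map to Week 12, and the ETD visit is used.

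**SAP 2.1.1.4, DLQI.** DLQI is not collected at every visit, so "The assessment window will be combined as Table 2-5". Week 12 becomes Day 30-85, and Week 24 is "Day 86 to Day 169". No tie rule is printed with this table.

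**Estimand.** SAP 1.2.2 gives DLQI 0-1 at Week 12 a similar approach to UAS7 ≤6, with treatment policy for discontinuation. SAP 2.6.3 says that retrieved drop-out (RDO) data are used. For diary scores, 2.1.1.4 repeats this: "The retrieved drop-out (RDO) data will be included in the weekly score derivation until Week 12, when treatment policy strategy is used for estimands". It has no such sentence for DLQI.

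**The concern.** The treatment-policy estimand asks for DLQI at Week 12 whether or not the participant is still on treatment. The protocol has sites collect that value from people who stop early, at a visit it calls SD. The remapping then removes the SD label and places the visit by study day. Because the DLQI window spans both the Week 8 and Week 12 visits, the ETD and SD assessments often fall in the same window. If the earliest is taken, the value from the day treatment stopped is reported as Week 12 and the post-discontinuation value is discarded.

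A second problem comes from the window edge and not from the tie rule. The DLQI Week 12 window closes on the scheduled day itself, while protocol section 8 asks only that visits be as close to the designated day as possible. A scheduled visit keeps its recorded number, but an SD visit does not. An SD return on Day 86 or later therefore becomes Week 24.

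At stake is whether one secondary endpoint, DLQI 0-1 at Week 12, is analysed as its estimand says.

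**Working it through.** **Step 1. Reproduce the SAP's examples with the Table 2-4 windows** (Week 4: Day 16-29; Week 8: 30-57; Week 12: 58-85).

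- ETD Day 35, SD Day 80: Week 8 and Week 12, no tie. Matches the SAP.
- Week 4 on Day 25, ETD Day 29: both Week 4, and the scheduled visit wins. Matches.
- ETD Day 58, SD Day 85: both Week 12, and the earliest (ETD) wins. Matches.

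**Step 2. Apply the same rule to the DLQI windows** (Tables 2-5 and 2-6: Day 2-29, 30-85, 86-169, 170-365).

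| ETD day | SD day | ETD maps to | SD maps to | Week 12 DLQI |
|---|---|---|---|---|
| 35 | 80 | Week 12 | Week 12 | Day 35 (tie rule) |
| 58 | 85 | Week 12 | Week 12 | Day 58 (tie rule) |
| 29 | 85 | Week 4 | Week 12 | Day 85 (correct) |
| 58 | 86 | Week 12 | Week 24 | Day 58 (window edge) |
| 29 | 86 | Week 4 | Week 24 | missing (window edge) |

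With SD on Day 85, the ETD value is used for every ETD day from 30 to 84. That is 84 − 30 + 1 = 55 days, and the value used is 85 − 84 = 1 to 85 − 30 = 55 days too early. If the return is recorded as the scheduled Week 12 visit, the first limb of the rule selects it and the problem disappears.

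**Step 3. Number of participants.** From SAP section 3: about 70 treated, about 15% dropout. Assumptions: all dropout is treatment stopping, spread evenly over 364 days.

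- Expected stops: 0.15 × 70 = 10.5.
- ETD on Day 30-84: 10.5 × 55/364 = 1.59 if all return; 0.79 if half return. This is the ceiling for substitution by the two mechanisms together.
- If half of the returns fall after Day 85 (assumption), the tie rule and the window edge account for 0.79 each, or 0.40 each if half return.
- Week 12 missing (ETD Day 2-29, SD after Day 85): 10.5 × 28/364 = 0.81 if every return is late; 0.40 if half are late; 0.20 if also only half return.
- Earlier dropout: if half of it (5.25) falls in the first 84 days, substitutions are 5.25 × 55/84 = 3.44, or 1.72 if half return.

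**Step 4. Effect on the rate.** Only a participant whose DLQI 0-1 status differs between the two visits changes the result. The documents do not give that share. At 10%, 25% and 50%, 1.59 substitutions give 0.16, 0.40 and 0.79 changed responses. Each moves the rate by 1/70 = 1.4 percentage points.

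For comparison, the SAP 5.4.1.2 interval at n = 70 and p = 0.5 (z² = 3.84) has lower limit (70 + 3.84 − 1 − 1.96 × √(3.84 − 2 − 1/70 + 4 × 0.5 × 36)) / (2 × 73.84) = 37.9%. By symmetry the upper limit is 62.1%, so the half-width is about 12 points.

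**The case against.** The strongest objection is that the SAP never says the tie rule applies to DLQI. The rule sits under a sentence listing vital signs and laboratory tests, and the ETD/SD examples use windows that DLQI does not have. The same section gives ECG its own restrictions on where ETD and SD visits may map, so one rule for all assessments cannot be presumed. SAP 2.6.3 covers DLQI and says RDO data will be used, so a programmer might follow that. The master analysis plan is not available, and parts of the SAP's patient-reported-outcome text are blanked out.

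Much of this stands. A reader might infer that the SAP instructs the earliest visit for DLQI, and the documents do not go that far. The application is an inference from three things: the subsection heading names DLQI, the rule refers to visits recorded in the eDiary (where DLQI is completed), and no other tie rule is visible. But 2.6.3 does not remove the problem, because it is the other half of the conflict. If the tie rule does not apply, the visible text gives no way to choose between the two values. What an unseen plan might say cannot be relied on in either direction.

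Two further points stand. The quoted tie rule accounts for only part of the 1.6; the rest comes from the window edge. And the count includes participants whom the composite strategy already sets to non-response (biologics before Week 12; cyclosporine or systemic corticosteroids after Week 8). For them the choice of visit does not matter, so the true number is lower by an amount the documents do not give.

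**Conclusion.** The point holds as a minor one. On the natural reading of SAP 2.1.1.4, a participant with an ETD visit on Day 30-84 and a return recorded as SD by Day 85 has the treatment-stop DLQI reported as Week 12, against the treatment-policy estimand. Independently of the tie rule, an SD return on Day 86 or later goes to Week 24. That leaves the ETD value standing as Week 12, or Week 12 missing.

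Under even dropout, substitution affects at most about 1.6 participants (0.8 if half return), fewer after the composite strategy. Front-loaded dropout could raise this to 3.4; even if all of those changed status in the same direction, the shift would be 3.44/70 = 4.9 points, within the 12-point half-width. No overall conclusion changes.

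A reader might infer that Week 12 efficacy in general is compromised, or that the DLQI rate is biased in a known direction. The documents support neither. UAS7, ISS7, HSS7 and AAS7 come from diary windows that include RDO data to Week 12, and adverse events are not windowed this way. Nothing shows whether DLQI would be better or worse at the later visit. All secondary analyses are descriptive (SAP 2.6.2).

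**What to change.** In SAP 2.1.1.4, for DLQI at Week 12 only:

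- If more than one remapped visit falls in Day 30-85 and none is recorded as the scheduled Week 12 visit, use the assessment closest to Day 85. For ETD Day 35 and SD Day 80 the distances are 50 and 5 days, so SD is used.
- State that the Day 58/Day 85 example does not apply to DLQI.
- Assign an SD visit made as the Week 12 return under protocol 9.1.1 but after Day 85 to Week 12, not Week 24, up to a fixed day named in the SAP. It then supplies the value in preference to an earlier ETD visit. Day 99 is one candidate, halfway to the Week 16 visit: (85 + 113)/2 = 99. This day is an assumption for the sponsor to set.

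A lone ETD visit stays remapped as now, and the safety windows are unchanged. The cost is a few lines of SAP text and programming, with no new data. The downside is that DLQI follows a different selection rule from the safety tables.
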